4.11 Immunogenicity Endpoints and Analyses

The proportion of participants who are negative for ADA at baseline with a positive ADA result on study, negative at baseline and remain negative, and positive ADA at baseline that increases or decreases in titer on study will be summarized. Samples with a positive ADA result may be evaluated for further immunogenicity including but not limited to neutralizing capacity. The incidence of neutralizing antibodies may be summarized if available. The impact of immunogenicity on safety, PK, and PD may be summarized and explored graphically.

4.12 Pharmacodynamic Endpoints and Analyses

Summary statistics for biomarkers, such as but not limited to those listed in CP-MGD020-01 Protocol Section 10.3 and corresponding changes from baseline, will be summarized and may also be presented graphically as will possible associations between changes in PD measures of interest and MGD020 alone or MGD020 and MGD014 dose and exposure.

4.12.1 Serum Cytokines

Data will be tabulated and summarized by dose panel and time. Plots of serum cytokine levels versus time may be provided. Additional analyses may be conducted in order to characterize the relationship between the MGD020 alone or MGD020 and MGD014 serum concentrations and serum cytokines (e.g., an exposure-response analysis), if deemed appropriate.

4.12.2 T-cell Binding

The percentages of cluster of differential CD4⁺ and CD8⁺ cells in blood with bound MGD020 (Part 1A) or bound with both MGD020 and MGD014 (Part 1B and Part 2) will be summarized over time. Values may also be presented graphically where appropriate.

4.12.3 T-cell Phenotype and Function

The percentages of CD4⁺ and CD8⁺ cells in blood with expression of activation markers (e.g., CD25, CD69, CD134, CD137), cytolytic markers (granzyme B, perforin), regulatory T cell marker (FoxP3), proliferation marker (Ki67), or memory subsets (naïve, central memory, effector memory, effector memory re-expressing CD45RA) will be summarized over time. Values may also be presented graphically where appropriate. Note that some biomarkers mentioned in the protocol amendment 1 have been removed and new biomarkers have been added here to reflect the change in terms of planned biomarker analyses.

4.12.4 Quantitative Viral Outgrowth Assay (QVOA)

In Part 2 only, for participants who complete the optional leukapheresis, changes in pre- and post-dose measurements of the frequency of resting CD4+ T-cell infection by QVOA will be assessed. Data will be reported as infectious units per million (IUPM) and 95% CI values will be determined from the maximum likelihood method. Statistical significance of changes in QVOA values following dosing will be evaluated by a nonparametric 2-sided exact sign test. The exact sign test used for this analysis makes minimal statistical assumptions and is based solely upon whether IUPM values decrease following dosing. As QVOA is a robust and reproducible assay, declines of more than 50% in QVOA values from serial measurements are infrequently seen and would be suggestive evidence for HIV-1 reservoir depletion.

4.12.5 Intact Proviral Deoxyribonucleic Acid Assay (IPDA)

In Parts 1A, 1B and 2, pre- and post-dose measurements of the frequencies of resting CD4+ T-cell infection by IPDA will be analyzed. Data will be reported as intact HIV-1 provirus per million CD4+ T-cells. 95% CIs for IPDA values will be determined and the statistical significance of changes following dosing will be evaluated by a nonparametric 2-sided exact sign test. Like QVOA, declines of more than 50% in IPDA values from serial measurements would be suggestive evidence for HIV-1 reservoir depletion.

4.12.6 Resting CD4+ T-Cell-Associated HIV-1 gag RNA

In Part 2 only, changes in pre- and post-dose measurements of rca-RNA will be assessed. TATA binding protein RNA will be used as the reference to normalize HIV gene expression given its reported stability across treatment conditions. Data will be log-transformed and Wilcoxon Two-Sample test will be used for statistical analysis of rca-RNA of pre- and post-DART treatment as previously reported.

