10.3.4 Persistent Human Immunodeficiency Virus-1

Measurements of persistent HIV-1 may include the following:

- Changes in pre- and post-dose measurements of the frequency of resting CD4+ T-cell infection by quantitative viral outgrowth assay (QVOA) in participants who complete the optional leukapheresis.
- Changes in pre- and post-dose measurements of the frequency of resting CD4+ T-cell infection by intact proviral DNA assay (IPDA).
- Changes in pre- and post-dose measurements of the level of resting CD4+ T-cell-associated HIV-1 gag RNA (rca-RNA).
- Changes in pre- and post-dose measurements of levels of residual low-level HIV-1 viremia quantified by single copy assay (SCA).

Although exposure to DART molecules in this study is brief, and latency reversing agents are not included in the experimental intervention at this time, there is a possibility that some persistently infected cells may be depleted. Exploratory assays are limited by blood volumes and the practical considerations of apheresis, but sufficient samples will be available to assess changes in IPDA, rca-RNA, and SCA. When possible, QVOA will be measured. In our experience, performing multiple assays, when possible, is desirable, given the biological and assay variations of these assessments.

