14.5.3.6 Resting CD4+ T-Cell-Associated HIV-1 gag RNA

In Part 2 only, changes in pre- and post-dose measurements of rca-RNA will be assessed. TATA binding protein RNA will be used as the reference to normalize HIV gene expression given its reported stability across treatment conditions (7). Data will be log-transformed and Wilcoxon Two-Sample test will be used for statistical analysis of rca-RNA of pre- and post-DART treatment as previously reported (13).

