b For participants who have been previously exposed to MGD014 or MGD020, obtain screening samples for ADA (MGD014 and MGD020) at least 21 days prior to enrollment to allow for results to be reported before enrollment.

c PK, ADA and cytokine samples may be obtained selectively at additional time points in participants who experience signs and symptoms of IRR or CRS.

Abbreviations: ADA: anti-drug antibody; CRS: cytokine release syndrome; EOI: end of infusion; EOS: end of study; HLA: human leukocyte antigen; IPDA: intact proviral DNA assay; IRR: infusion related reaction; N/A: not applicable; PBMC: peripheral blood mononuclear cell; PD: pharmacodynamic; PK: pharmacokinetic.

Table 11 Pharmacokinetic, Immunogenicity, and Pharmacodynamic Sampling Schedule: Part 2

Study Day	Time Point	Window	PK ^a (Serum)		ADA (Serum)		Cytokines (Serum)	PD: T-cell Binding & Phenotype (Whole Blood)	PD: IPDA & rca- RNA (PBMCs)	HLA Typing (Whole Blood)	PD: QVOA (Leuka- pheresis)	PD: SCA (Plasma)
			MGD020	MGD014	MGD020	MGD014						
-56 to -1	Screening	N/A			X ^b	X ^b					X ^c	
1	Pre-MGD020 infusion	N/A	X	X			X	X	X	X		X
1	EOI MGD020	+ 10 min	X									
1	EOI MGD014	+ 10 min		X								
1	1 h after EOI MGD014	± 5 min	X	X			X	X				
1	4 h after EOI MGD014	± 5 min	X	X			X	X				
2	No specific time	N/A	X	X			X	X				
4	No specific time	N/A	X	X								
8	No specific time	± 1 day	X	X			X	X				
15	Pre-MGD020 infusion	N/A	X	X	X	X	X	X				
15	EOI MGD020	+ 10 min	X									
15	EOI MGD014	+ 10 min		X								
15	4 h after EOI MGD014	± 5 min	X	X			X	X				
29	Pre-MGD020 infusion	N/A	X	X	X	X	X	X				
29	EOI MGD020	+ 10 min	X									
29	EOI MGD014	+ 10 min		X								
29	4 h after EOI MGD014	± 5 min	X	X			X	X				
43	No specific time	± 2 days	X	X					X		X ^c	X
50	No specific time	± 2 days	X	X								
64	No specific time	± 3 days	X	X								
IRR-CRS ^d	No specific time ^d	N/A	X	X	X	X	X					
78/EOS	EOS	± 3 days	X	X	X	X						X

a Obtain pre-infusion PK samples before start of infusion on visit day (dosing day) or day before. When collecting multiple samples, collect PK sample first.

b For participants who have been previously exposed to MGD014 or MGD020, obtain screening samples for ADA (MGD014 and MGD020) at least 21 days prior to enrollment to allow for results to be reported before enrollment.

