4.9 Exploratory Endpoints and Analyses

The endpoints described in Sections 4.12.2-4.12.7 below are exploratory and only include participants from one or multiple parts of the study. The described analyses of these endpoints are optional and may not be performed if sample size does not permit.

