4.12.7 Plasma Viremia by Single Copy Assay (SCA)

In Part 2 only, changes in pre- and post-dose measurements of levels of residual low-level HIV-1 viremia quantified by SCA will be assessed. Data will be reported as HIV-1 copies per mL plasma. 95% CIs for the SCA values will be determined and the statistical significance of changes following dosing will be evaluated by a nonparametric 2-sided exact sign test.

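### Pre- and post-dose rca-RNA from the same Part 2 participants (at most 6) is compared with an unpaired Wilcoxon test, which can hide a consistent fall

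*SAP*

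**What the plan says.** For rca-RNA, assessed in Part 2 only, SAP 4.12.6 specifies: "Data will be log-transformed and Wilcoxon Two-Sample test will be used for statistical analysis of rca-RNA of pre- and post-DART treatment". The method is justified by reference to an earlier report. Protocol 14.5.3.6 names the same test. Neither document gives a significance level, says whether the test is one- or two-sided, or states the unit of analysis for this assay.

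Protocol 10.3.4 and the opening sentence of SAP 4.12.6 both define the quantity of interest as the change between pre- and post-dose measurements. Protocol Appendix 2, Table 11, as we read it, takes the sample before infusion on Day 1 and again on Day 43. Part 2 is one cohort of up to 6 participants with no control arm (SAP 3.4 and 4.3).

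The parallel assays are handled differently. For QVOA the plan is: "Statistical significance of changes in QVOA values following dosing will be evaluated by a nonparametric 2-sided exact sign test". IPDA (SAP 4.12.5) and SCA (SAP 4.12.7) use the same test, which respects the pairing. SAP 4.12 adds that biomarkers and "corresponding changes from baseline, will be summarized". On status, SAP 4.9 says: "The described analyses of these endpoints are optional and may not be performed if sample size does not permit". SAP 4.3 and Protocol 14.1 also state that the study will calculate no inferential statistics.

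**The concern.** The Wilcoxon two-sample (rank-sum) test assumes two independent groups. Here each pre-dose value has a partner from the same person. If people start at very different levels, their pre- and post-dose values interleave in the pooled ranking, and a fall seen in everyone barely moves the rank sum. The planned log transform does not help, because it leaves the ranks unchanged.

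A consistent fall could therefore be reported as non-significant only because baselines differ. Exploratory results may be left out of the study report unless they are judged meaningful (Protocol 3.3, SAP 2.3), so the choice of test could influence whether the result is reported at all. SAP section 5 excludes these analyses from the shells in the programming plan, which leaves the SAP as the main place where the method is fixed in advance.

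**Working it through.** **Design figure.** The only sample-size figure in the plan reproduces: 3×(1+3) + 3×(3+3) = 30 in Part 1A, 3×6 = 18 in Part 1B and 1×6 = 6 in Part 2, total 54. So rca-RNA has at most 6 pairs. A two-sided alpha of 0.05 is assumed below, since none is stated.

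**Worked example (invented values).** The 50% fall is the benchmark that the plan uses for QVOA and IPDA; none is given for rca-RNA.

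- Pre: 10, 22, 46, 95, 210, 430
- Post/pre ratio: 0.47, 0.53, 0.50, 0.48, 0.52, 0.50
- Post: 4.7, 11.66, 23, 45.6, 109.2, 215

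*Rank-sum.* The number of post values lying below each pre value is 1 + 2 + 4 + 4 + 5 + 6, so U = 22 out of 36. The exact two-sided p over the C(12,6) = 924 allocations is 0.59, on raw or log values.

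*Paired.* All six fall, so the exact sign test gives 2×0.5^6 = 0.031, and the signed-rank test gives the same.

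*Estimate.* The log10 ratios have mean −0.301 and SD 0.0198. The half-width is 2.571×0.0198/√6 = 0.021. The geometric mean ratio is 0.50 (95% CI 0.48 to 0.52).

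**Dependence on baseline spread.** Six evenly spaced baselines with falls of 47% to 53% give these exact rank-sum p-values. The paired p is 0.031 throughout.

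| Baseline range | Rank-sum p |
|---|---|
| 1.6-fold | 0.002 |
| 2.5-fold | 0.009 |
| 3.7-fold | 0.065 |
| 8- to 19-fold | 0.24 |
| 50-fold or more | 0.70 |

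**Simulation.** n=6, true change log10(0.5) = −0.301, exact two-sided tests, 40,000 runs per cell. The documents give no rca-RNA variability, so the SDs (log10) are assumptions.

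| Between-SD / within-SD | Rank-sum | Paired t on log10 | Signed-rank or sign |
|---|---|---|---|
| 0 / 0.15 | 83% | 79% | 61% |
| 0.15 / 0.15 | 56% | 79% | 61% |
| 0.3 / 0.15 | 19% | 79% | 61% |
| 0.7 / 0.15 | 1% | 79% | 61% |
| 0.3 / 0.20 | 16% | 56% | 39% |
| 0.7 / 0.20 | 1% | 55% | 39% |

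The last column can be checked directly. At n=6 both tests need all six to move the same way. P(one participant falls) = Φ(0.301/(√2×within-SD)) = 0.922 or 0.856, and the sixth powers are 0.61 and 0.39. With no true change and between-SD 0.3 to 0.7, the rank-sum test rejects in at most 0.4% of runs, so the error is towards missing a fall.

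**Smallest attainable two-sided p.** Rank-sum: 2/C(2n,n). Sign test: 2×0.5^n, and signed-rank has the same floor.

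| n | Rank-sum | Sign or signed-rank |
|---|---|---|
| 3 | 0.10 | 0.25 |
| 4 | 0.029 | 0.125 |
| 5 | 0.008 | 0.0625 |
| 6 | 0.002 | 0.031 |

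**Consequence for QVOA and SCA.** With fewer than 6 untied pairs the planned sign test cannot reach 0.05. With 6 it does so only if all agree; 5 of 6 gives 0.22. QVOA depends on optional leukapheresis (Protocol 9.10). If each of six participants independently completes both procedures with probability 0.7 to 0.9 (assumed), all six pairs exist with probability 0.7^6 = 0.12 to 0.9^6 = 0.53.

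**The case against.** The strongest objection is that the unit of analysis is unknown. Both documents defer to an earlier report that cannot be consulted here. If that method compares replicate measurements within one participant, the pairing argument does not apply in this form. This stands as a limit, but neither document mentions replicates for rca-RNA, and replicate wells would be clustered within participant. The text needs correcting or completing either way.

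Second, the p of 0.59 comes from invented values with a 43-fold baseline range. With tightly clustered baselines the rank-sum p (0.002) is smaller than the paired one. That is true, and the size of the loss is therefore conditional. For the listed baselines, 0.59 is the most common result when falls of 47% to 53% are assigned in different orders; the range is 0.39 to 0.70.

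Third, at n=4 or 5 a sign or signed-rank test can never reach 0.05, whereas the planned test can. This rules out a nonparametric paired test as the sole replacement. It does not rule out the paired log-change interval. At those sizes the paired t test has more power than the rank-sum test in every setting tried with between-SD 0.15 or more, and is within about 2 points of it at between-SD 0.

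Fourth, changes from baseline will be summarised in any case, and the analysis is exploratory, optional and conservative. A careful reader might see the fall in the summaries, and no false claim of activity is likely. This limits the seriousness but does not make the test right.

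**Conclusion.** The test named for rca-RNA does not match a within-participant endpoint, and it is out of step with the plan's own treatment of QVOA, IPDA and SCA. If the participant is the unit and baselines vary by 0.3 to 0.7 log10 (assumed), power to detect a 50% fall at n=6 drops from 55% to 79% with a paired t test to 1% to 19%. The loss shrinks as baselines become more alike and is absent when they do not differ. The change should be made, but no primary or secondary conclusion depends on it.

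Two smaller points follow from the same sections. A non-significant sign test for QVOA or SCA with 5 or fewer untied pairs carries no information and must not be read as no change; SAP 4.9 allows analyses to be dropped for small numbers but gives no threshold. The statement that no inferential statistics will be calculated also conflicts with the tests in SAP 4.12.4 to 4.12.7. SAP 4.1, which calls most but not all summaries descriptive, softens that conflict without removing it.

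**What to change.** **SAP 4.12.6 and Protocol 14.5.3.6.** Replace the two-sample test with an analysis of each participant's log10 change (Day 43 minus Day 1). Report the geometric mean post/pre ratio, its 95% CI from a paired t analysis, and the individual values. State the unit of analysis; if replicate wells are used, average them per participant or allow for clustering. State how undetectable values enter the log change.

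**SAP 4.12.4 and 4.12.7.** The sign test may stay as supportive. For QVOA add an estimate of within-participant change with a CI. For SCA add individual changes, a rule for undetectable values, and the post-dose time point, since Table 11 has both Day 43 and Day 78. In both, say that the sign test is not interpreted with fewer than 6 untied pairs.

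**SAP 4.12.5.** State whether IPDA is pooled across parts, because the six-pair floor need not apply if it is.

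**SAP 4.3 and Protocol 14.1.** Limit the statement on inferential statistics to the primary and secondary endpoints.

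**Cost.** Wording in these sections and code for the separately reported exploratory analyses; no new samples. The rule for undetectable values must be agreed before data are seen. The paired interval assumes roughly normal log ratios and will be wide. Its half-width on the log10 scale is t(0.975, n−1)×within-SD×√(2/n). With within-SD 0.15 to 0.20 that is a factor of about 1.7 to 2.0 either way at n=6, and 3.4 to 5.0 at n=3.

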4.12.7 Plasma Viremia by Single Copy Assay (SCA)

In Part 2 only, changes in pre- and post-dose measurements of levels of residual low-level HIV-1 viremia quantified by SCA will be assessed. Data will be reported as HIV-1 copies per mL plasma. 95% CIs for the SCA values will be determined and the statistical significance of changes following dosing will be evaluated by a nonparametric 2-sided exact sign test.

5 LIST OF TABLES, LISTINGS, AND FIGURES

The list of tables, listings, and figures (TLFs) and associated shells planned for the CSR based on the analyses described in this SAP will be provided in a separate SPP, which will also include data reporting conventions and programming specifications for the development of these TLFs. Note that the SPP will not include TLF shells for the exploratory analyses described in Sections 4.12.2-4.12.7 as they will be performed and reported separately.
